3.1 Data export

Data are entered in the SecuTrial EDC system. Data will be exported using the SecuTrial data export tool, as semicolon delimited file, and are labelled using the codebook provided by the same export by an unblinded statistician. Further, all analysis sets need to be defined by the unblinded statistician, since adherence to the study (needed to define analysis sets) is recorded in the “smoking and e-cigarettes” (cig_ecig) form, from which the treatment group becomes instantly obvious.

The unblinded statistician needs to provide datasets to the blinded statistician without any direct or indirect information about the group allocation but an encoded group allocation variable will be provided.

3.2 Data validation

Data validation will follow the principles defined in the SOP Statistical data validation.

All variables used in the analysis, including the derived variables, will be checked for:

- Missing values (frequency per parameter, consistency between related parameters within patient, report on missing values for parameters where no missing values were allowed) including responses such as “unknown”, “no answer”, “unspecific”, etc.
- Identification of duplicates
- Outliers (range of values (univariate or multivariate), shape of frequency distribution of data, extremes (inspection of data below the 2.5th and above the 97.5th percentile, i.e. data points on both ends of their cumulative distribution))
- Inconsistencies (chronological dates, suspiciously high frequencies of first day of month, first day of the year, in order to investigate whether incomplete time or date variables were cut)
- Consistency in the measurement units and consistency between variables

For multi-centre trials any of the above items should be analyzed separately by centre and then compared.

All deviations will be queried if no appropriate comment is given in the SecuTrial EDC database system.

A report will be produced which documents:

- The types of quality checks implemented
- The findings (including the distinction between clearly wrong and suspicious data)
- The date and/or database version the checks were applied to.

CTU Bern	SAP for: ESTxENDS	Version: 4-02.0	
CTU Bern	Template: Statistical Analysis Plan (SAP)	Version: 03	
	Code: CS_STA_TEM-11	Valid from: 28-02-2019 5.6.2023	Page 9 of 27

4. Statistical principles

4.1 Confidence intervals and *P* values

All applicable statistical tests will be 2-sided and will be performed using a 5% significance level. Estimates and effect measures will be presented with a two-sided 95% confidence interval.

4.2 Analysis populations

This document describes the patient populations and estimands that are used for the primary and secondary analysis or primary and secondary outcomes. Further patient sets and estimands may be addressed in further exploratory analyses, which will not be done by CTU Bern but by the sponsor-investigator.

4.2.1 Full analysis set (FAS)

The full analysis set (FAS) will include all randomized subjects. Following the intention-to-treat principle, subjects will be analysed according to the treatment they are assigned to at randomization, regardless of any protocol violations or discontinuations of the intervention.

4.2.2 Per-protocol (PP)

The per-protocol population consists of all subjects in the FAS who do not have any protocol deviations that could confound the interpretation of analyses conducted on the FAS. The following are common major protocol deviations:

TABLE 1: DERIVATION OF PROTOCOL DEVIATIONS.

Protocol deviation	eCRF sheet	Variable	Variable type	Derivation
Violation of inclusion or exclusion criteria				
Age is less than 18 years	eligibility	ic_age18	Continuous: years	ic_age18 == No
Smoking of less than 5 cigarettes a day	eligibility	ic_cigmore5, ic_cigday,	binary, continuous, continuous	ic_cigmore5 == No OR ic_cigday < 5
Non adherence to intervention				
Regular use of an ENDS or tobacco heating systems device in the control group (on a minimum of 5 days during the last 7 days, on at least 1 visit)	cig_ecig [day 0, week 1, 2, 4, 8, month 6]	quit_ecig_use, quit_ecig_7days, quit_ecig_7d_nxwk	binary, binary continuous	sum(quit_ecig_use == Yes AND quit_ecig_7days == Yes AND quit_ecig_7d_nxwk >= 5) >= 3 visits
No regular use of ENDS or tobacco heating systems device in the intervention group (a minimum of 5 days during	cig_ecig [week 1, 2, 4, 8, month 6]	quit_ecig_use, quit_ecig_7days, quit_ecig_7d_nxwk,	binary binary continuous	sum(quit_ecig_use == No OR (quit_ecig_7days == Yes AND quit_ecig_7d_nxwk < 5)) == 0 visits

CTU Bern

SAP for: ESTxENDS

 Version: [4.02.0](#)

CTU Bern

Template: Statistical Analysis Plan (SAP)

Version: 03

Code: CS_STA_TEM-11

 Valid from: [28.02.2019](#) to [05.06.2023](#)

Page 10 of 27

Protocol deviation	eCRF sheet	Variable	Variable type	Derivation
the last 7 days, on at least 1 visit is required)				
Primary outcome is outside of time window of 152 to 264 days from target quit date (180 days -4/+12 weeks) or missing	Smoking, smoking + E-cigarette	cig_quitdate, mnpvisfdt	binary	cig_quitdate- mnpvisfdt >=152 AND cig_quitdate- mnpvisfdt <=264

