Participants in the additional MRT data collection at the 6 month visit will receive 90 CHF given that these are additional measures and that participants will need to come back on another day. The 90 CHF corresponds to 2X1.5 hours visits a 25 CHF per hour (75 CHF) and 15 CHF for transportation costs. Healthy volunteers will receive a voucher of 90CHF and a voucher for a lunch at the Inselspital, Bern.

At 12- and 24- months follow-up, we will offer a voucher to all participants coming for a personal visit worth 30 CHF in order to encourage them to come at the clinical visit in person to assess and validate outcomes.

Adherence to the allocated product is defined as not having used the non-allocated product on a minimum of 5 days during the last 7 days, on at least 1 visit.

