4.3.2 Principal strata estimand

Outcome of interest: The secondary analysis of the primary outcome (binary) will focus on the principal strata estimand

Patient set of interest: using the per protocol analysis set. Subjects with protocol violations will be excluded from the analysis.

Intercurrent events: Intercurrent events will be disregarded. Missing values in the primary outcome will be categorized as persistent smoker (i.e. treatment failures).

Summary measure: The difference between the two groups will be presented as a relative risk.

CTU Bern	SAP for: ESTxENDS	Version: 4.02.0
----------	-------------------	---------------------------------

CTU Bern	Template: Statistical Analysis Plan (SAP)	Version: 03
	Code: CS_STA_TEM-11	Valid from: 28.02.2019 to 06.2023

5. Trial Population

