5.6 Adherence and protocol deviations

Adherence

Adherence in the control group is defined as not having used an ENDS device on 5 or more days during the last 7 days of any visit.

Adherence in the intervention group is defined as having used an ENDS device on 5 or more days during the last 7 days of at least one visit.

Adherence will be presented in a table as number (and %) of patients not smoking cigarette, smoking cigarettes only, smoking ENDS only, and smoking cigarettes and ENDS for both groups at each time point (Weeks 1, 2, 4, 8, and month 6). In addition, the number (and %) of patients using any NRT (patches, gums) or other smoking cessation medication (bupropion, varenicline) during the 24 hours before the visit will be presented in a similar table.

Protocol deviations

Protocol deviations are defined in Table 1. All of these protocol deviations will be presented in a table with the number of patients (%) having a protocol deviation for the control and intervention group.

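### Three of the five derivations in SAP Table 1 contradict the deviations they are meant to code, so the per-protocol set as coded is not the set the SAP defines

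*Supplement*

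**What the plan says.** SAP 2.0 section 4.2.2 defines the set by exclusion: "The per-protocol population consists of all subjects in the FAS who do not have any protocol deviations" that could confound the interpretation. Table 1 then gives each deviation in words and, in a Derivation column, as an expression in eCRF variables. Section 4.3.2 applies it to the secondary analysis: "Subjects with protocol violations will be excluded from the analysis".

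The three rows at issue read as follows.

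- **Intervention arm.** In words, regular use (at least 5 of the last 7 days) at one visit or more is enough. Section 5.6 agrees, defining adherence as "having used an ENDS device on 5 or more days during the last 7 days of at least one visit". The derivation is "sum(quit_ecig_use == No OR (quit_ecig_7days == Yes AND quit_ecig_7d_nxwk < 5)) == 0 visits", over weeks 1, 2, 4, 8 and month 6.
- **Control arm.** In words, regular use at one visit or more is a deviation, and section 5.6 says the same. The derivation ends "quit_ecig_7d_nxwk >= 5) >= 3 visits", over day 0 to month 6.
- **Time window.** In words, the deviation is a primary outcome outside 152 to 264 days from the target quit date, or missing. The derivation is "cig_quitdate- mnpvisfdt >=152 AND cig_quitdate- mnpvisfdt <=264".

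Protocol 9.0 section 8.4 gives a further definition: "Adherence to the allocated product is defined as not having used the non-allocated product", with the same threshold of 5 of 7 days at one visit or more.

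**The concern.** The Derivation column names variables and thresholds, so it is what a programmer would implement. In three of five rows it selects different people from those the adjacent text and section 5.6 describe.

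The per-protocol set is the population for the secondary analyses (section 6.3.2) and for one of the two sets of safety tables (sections 4.2.3 and 6.6). Table 1 also feeds the table of protocol deviations by arm (section 5.6). An analyst following the code would report a per-protocol effect for a group the SAP did not intend. An analyst following the words would depart from the written derivation. Because SAP 2.0 leaves all analyses to an unblinded team, the plan should not hold two competing definitions of an analysis set.

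**Working it through.** **Polarity of the column.** The cigarette row is "ic_cigmore5 == No OR ic_cigday < 5", which is true when the criterion is violated. The age row works the same way. TRUE therefore means deviation, and the other rows are read on that basis.

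**Window limits.** 180 − 28 = 152 and 180 + 84 = 264, so the stated limits reproduce.

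**Intervention row.** Evaluate the expression over the five contacts.

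- Regular use at all five: count of non-regular contacts = 0, so flagged and excluded. In words this person is adherent.
- No use at any: count = 5, so not flagged and kept. In words this person is non-adherent.
- If each contact is either regular use or no use, there are 2^5 = 32 patterns. The code flags only the all-regular pattern and keeps the only non-adherent one.
- With four states per contact (regular; used on fewer than 5 days; used but not in the last 7 days; no use) there are 4^5 = 1024 patterns. By the wording, 3^5 = 243 are non-adherent. The code keeps 242 of these and excludes 31 of the 1024 − 243 = 781 adherent ones. These are counts of patterns, not of people.

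**Control row.** With six contacts, each regular or not, there are 2^6 = 64 patterns. The wording flags 63 and the code flags 42. The 21 missed are those with one regular-use visit (6) or two (15).

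**Window row.** Take mnpvisfdt as the month-6 visit date; the SAP does not define it. A visit on day 180 gives quit date minus visit date = −180, which is not ≥ 152. Any visit after the quit date gives a negative value, so the expression is never true. With the subtraction reversed it would flag days 152 to 264 and miss days 151 and 265. Read instead as a condition for retention, the expression as signed would exclude everyone. No term covers a missing outcome.

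**Illustration of size.** Inputs are the expected 6-month counts in Protocol Table 11.2-1, leaving out the 29 per arm lost to follow-up.

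- Intervention: 56 quit with ENDS, 111 smoke with ENDS, 50 quit without, 340 smoke without.
- Control without ENDS, used as comparator throughout: 56 quit, 473 smoke, so 56/529 = 10.6%.
- As coded, if all 6-month ENDS users were regular at every contact and nobody else was excluded: 50/(50 + 340) = 50/390 = 12.8%; RR = 12.8/10.6 ≈ 1.2.
- In words, if only the 6-month users ever used regularly: 56/(56 + 111) = 56/167 = 33.5%; RR ≈ 3.2.
- In words, if every followed participant used regularly at least once: (56 + 50)/557 = 106/557 = 19.0%; RR ≈ 1.8.

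The set in words moves between the last two figures as earlier users who had stopped by month 6 are added, provided they quit smoking at the same 12.8% as the rest of the group without ENDS. These are two scenarios, not strict bounds.

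**The case against.** The strongest reply is that this is a coding slip in a secondary population. The primary analysis uses the full analysis set and is untouched, and safety is also reported by intention to treat. The intended adherence rule is stated in words twice, consistently, in Table 1 and section 5.6. The validation of derived variables (section 3.2) and the deviation table might expose the error, for example through a window-deviation count of zero. All of that stands, and it limits the reach of the point. It does not remove it: double programming (section 6.9) covers only the primary analysis, two programmers given the same faulty expression would agree, and neither Table 4 nor the closing list of SAP changes corrects the rows.

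Stronger readings are tempting, and the documents do not support them:

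- A reader might infer that the whole table is inverted. Two rows are correct, and the control row is a threshold mismatch. It concerns regular use, not any vaping.
- A reader might infer that the coded intervention group is nearly the reverse of the intended one. The code drops only people with no recorded non-regular contact. Adherent participants with even one recorded contact of no use, or of use on fewer than 5 days, stay in. The share of all-contact users is not given.
- A reader might take 33.5% (RR about 3.2) as the result for the defined set. That set needs regular use at only one of five contacts, whereas Table 11.2-1 shows use at 6 months only.
- A reader might say that heated-tobacco use is coded as adherence. Only the row label says so; the expression uses the e-cigarette variables.

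Whether a set chosen by observed use deserves the principal-strata label is a separate estimand question, and this point does not rest on it.

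**Conclusion.** The contradiction is real and is shown by logic alone for the intervention and control rows. For the window row it also assumes that mnpvisfdt is the month-6 visit date. As written, the code excludes all-contact regular users and keeps never-users in the intervention arm, keeps controls with regular use at one or two visits, and flags no out-of-window or missing outcome.

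The effect on estimates cannot be fixed from the documents. Under the stated assumptions the illustrative relative risk is about 1.2 as coded, against roughly 1.8 to 3.2 for the set in words, so the choice of column could matter materially for the per-protocol result. The trial's primary conclusion does not depend on it. Nothing in the documents shows which version was programmed, so no inference about the reported per-protocol results follows.

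**What to change.** Replace the three expressions. Let R be the number of visits with quit_ecig_use == Yes AND quit_ecig_7days == Yes AND quit_ecig_7d_nxwk >= 5.

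- Intervention deviation: R == 0 over weeks 1, 2, 4, 8 and month 6. State how an unrecorded visit counts.
- Control deviation: R >= 1 over day 0 to month 6.
- Window deviation: (mnpvisfdt − cig_quitdate) < 152 OR > 264 OR missing, with mnpvisfdt defined. First reconcile the missing-outcome exclusion in Table 1 with section 4.3.2, which keeps missing primary outcomes in the per-protocol analysis as persistent smokers. Both cannot hold.

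Reconcile the adherence definition in Protocol 8.4 with SAP 5.6: under 8.4 an intervention participant who never vapes need not be non-adherent. Also reconcile the tobacco heating systems in the Table 1 row labels with the ENDS-only wording of 5.6.

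The cost is a wording change and a recode, then a rerun of the per-protocol, per-protocol safety and deviation tables. No new data are needed.

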4.2.3 Safety population

Safety data will be analysed in the ITT and PP patient sets. Moreover, separate listings of all the serious adverse events (SAEs) and adverse events (AEs) according to the consumption preceding the event (cigarettes, ENDS, both, none) will be provided.

4.3 Estimands

4.3.1 Treatment policy estimand

Outcome of interest: The primary analysis of the primary outcome (binary) will focus on the treatment policy estimand,

Patient set of interest: using the full analysis set following the intention-to-treat principle, i.e. subjects will be analysed according to the randomized group, irrespective of the treatment actually received.

Intercurrent events: Intercurrent events will be disregarded. Missing values in the primary outcome will be categorized as persistent smoker (i.e. treatment failures).

Summary measure: The difference between the two groups will be presented as a relative risk.

The primary analysis of secondary outcomes will focus on the treatment policy estimand as well. Missing values in secondary smoking cessation outcomes will be treated as for the primary outcome. Missing values in other outcomes will be imputed. Effect sizes of binary outcomes will be presented as relative risk. Effect sizes of continuous outcomes will be presented as mean difference.

4.3.2 Principal strata estimand

Outcome of interest: The secondary analysis of the primary outcome (binary) will focus on the principal strata estimand

Patient set of interest: using the per protocol analysis set. Subjects with protocol violations will be excluded from the analysis.

Intercurrent events: Intercurrent events will be disregarded. Missing values in the primary outcome will be categorized as persistent smoker (i.e. treatment failures).

Summary measure: The difference between the two groups will be presented as a relative risk.

CTU Bern	SAP for: ESTxENDS	Version: 4.02.0
----------	-------------------	---------------------------------

CTU Bern	Template: Statistical Analysis Plan (SAP)	Version: 03
	Code: CS_STA_TEM-11	Valid from: 28.02.2019 to 06.2023

5. Trial Population

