6.3.2 Secondary analyses

Secondary analyses are based on the principal strata estimand, using the per-protocol analysis set. Binary outcomes will be presented as proportion with 95% Wilson confidence interval in each intervention group and compared between groups using the chi-square test. Effect sizes will be presented as relative risk with 95% Koopman confidence interval, as well as risk difference with 95% Newcombe-hybrid-score confidence interval. Continuous outcomes will be analysed using linear models, adjusted for outcome measures at baseline, if available, with mean differences (95% confidence interval) as effect sizes. If secondary outcomes are missing, we will use the imputed datasets generated for the primary analysis.

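### SAP 2.0 calls its secondary analysis a principal strata estimand but defines no stratum and plans an unadjusted per-protocol comparison of two differently selected groups, which does not estimate one

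*Supplement*

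**What the plan says.** SAP 2.0 section 4.3.2 says: "The secondary analysis of the primary outcome (binary) will focus on the principal strata estimand". The patient set is given as "using the per protocol analysis set. Subjects with protocol violations will be excluded from the analysis". Intercurrent events are to be disregarded, and missing primary outcomes are counted as smoking. No group is defined by what a participant would do under each allocation.

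Section 6.3.2 extends this to all secondary analyses: "Secondary analyses are based on the principal strata estimand, using the per-protocol analysis set". Binary outcomes are compared with a chi-square test and an unadjusted RR and RD. Continuous outcomes use a linear model adjusted only for the baseline value.

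Table 1 in section 4.2.2 filters the arms in opposite directions. In the control arm the deviation is "Regular use of an ENDS or tobacco heating systems device in the control group". In the ENDS arm it is "No regular use of ENDS or tobacco heating systems device in the intervention group". A missing or out-of-window primary outcome is also a deviation in either arm. Section 5.6 matches the device-use rules: "Adherence in the intervention group is defined as having used an ENDS device on 5 or more days during the last 7 days"; one such visit is enough. For controls, adherence means that no visit shows use at that level.

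Protocol 9.0 section 11.4.3 plans only modified per-protocol sensitivity analyses, mainly with control participants who start ENDS in mind. It does not use the principal-stratum label.

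**The concern.** A principal stratum is one kind of person present in both arms, defined by behaviour under both allocations. An example is people who would vape regularly if given ENDS and would not otherwise. Randomisation balances such a stratum, so an effect within it is causal.

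The planned comparison does not isolate any such stratum. It conditions on observed use, with a different condition in each arm. People who never take up ENDS leave the ENDS arm but stay in the control arm. If they differ from the others in their chance of quitting, the RR departs from 1 even when ENDS does nothing.

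At stake is the interpretation of every per-protocol result, since section 6.3.2 applies this analysis to the primary and secondary outcomes alike. A reader who sees the label may take the RR as the effect in adherers.

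**Working it through.** **The plan's own figure.** The documents give no figure for this analysis. The planning figure for the primary outcome reproduces. The unpooled normal approximation for 12% v 19%, two-sided alpha 0.05 and 90% power is (1.960 + 1.282)² × (0.12×0.88 + 0.19×0.81) / 0.07², which rounds up to the stated 557 per group. Then 1114 / 0.95 = 1172.6, against the stated 1172.

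**Who is kept.** Assume that nobody would vape regularly only if allocated to control.
- ENDS arm, regular users kept: compliers plus always-users.
- Control arm, regular users removed: compliers plus never-users.

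**Inputs.**
- Quit rate 12% in both arms, i.e. no ENDS effect. This is the expected control rate in protocol section 11.2.
- Control participants removed for regular use: 5%, quitting at 12%. The 5% is the protocol's expected share buying ENDS, used here as a stand-in.
- Share f of the ENDS arm removed, and its quit rate q: not in the documents. Here f = 20% and q runs from 6% to 18%.
- Further control share m removed as dropouts (all counted as smokers under intention to treat): 0% to 15%. The protocol plans 5% loss in each arm. The history of changes reports selective withdrawal in the control group but no percentage.

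**Formulas.** ENDS-arm rate = (0.12 − f·q)/(1 − f). Control rate = (0.12 − 0.05×0.12)/(0.95 − m) = 0.114/(0.95 − m).

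**Check by strata** (f = 20%, q = 6%, m = 0). Never-users are 20% at 6%, always-users 5% at 12%, and compliers 75% at (0.12 − 0.012 − 0.006)/0.75 = 13.6%.
- Kept ENDS arm: (0.006 + 0.102)/0.80 = 13.5%.
- Kept control arm: (0.012 + 0.102)/0.95 = 12.0%.
- RR = 1.125, while the complier RR is 1.00.

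**Results.** The last two columns are the percentages of 20,000 simulated trials (586 per arm) significant in each direction. The nominal value is 2.5% each.

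| q | m | ENDS rate | Control rate | RR | Favours ENDS | Favours control |
|---|---|---|---|---|---|---|
| 6% | 0% | 13.5% | 12.0% | 1.12 | 11.0% | 0.4% |
| 12% | 0% | 12.0% | 12.0% | 1.00 | 2.4% | 2.4% |
| 18% | 0% | 10.5% | 12.0% | 0.87 | 0.4% | 11.2% |
| 6% | 5% | 13.5% | 12.7% | 1.07 | 5.6% | 0.9% |
| 6% | 10% | 13.5% | 13.4% | 1.01 | 2.8% | 2.3% |
| 6% | 15% | 13.5% | 14.2% | 0.95 | 1.1% | 5.3% |

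The rows with m above zero add no separate dropout removal in the ENDS arm. At f = 30% the RR is 1.21 with q = 6% and 0.79 with q = 18%.

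**Evidence on direction.** Protocol Table 11.2-1 expects 56/167 = 33.5% quitting among ENDS-arm users at 6 months and 50/390 = 12.8% among non-users. Use and quitting are thus expected to go together. These figures mix effect with selection, and use at 6 months is not regular use at one visit or more. They cannot supply f or q.

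**The case against.** Four points weigh on the other side.

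- **A secondary analysis.** The primary analysis is intention to treat on the full analysis set, and SAP section 4.2 leaves room for further estimands in exploratory work. This stands and limits the point to the per-protocol results.
- **Direction.** A reader might infer that the comparison favours ENDS and inflates false positives for it. The documents do not support that. They give neither the share removed for non-use nor its quit rate, and the requirement of regular use at only one visit may remove few people. Table 1 also removes missing outcomes, and heavier control dropout pushes the RR down. The literal coding matters too: it flags an ENDS-arm participant when the count of visits with no or irregular use is zero, which would remove consistent users. It flags a control participant only from three visits of regular use, not one. Under that coding the selection changes and could work against ENDS. The arms would still be filtered differently and no stratum would be defined, so the label would still be wrong.
- **Reporting.** A reader might also infer that the result will be published as a causal effect in adherers. No section says so; section 6.3.2 promises proportions, RR and RD. The label invites that reading but does not state it.
- **Weights.** Section 6.5 adds stabilised weights, but for censoring or outcome data and not for selection on adherence. They do not close the gap.

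**Conclusion.** The mismatch holds on the text of SAP 2.0. Sections 4.3.2 and 6.3.2 name a principal strata estimand, define no stratum, state no identifying assumption, and estimate it by comparing groups that are not the same stratum. The resulting RR and RD are not a principal-stratum effect.

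What the documents do not settle is the direction and size of the bias. With no ENDS effect, the illustrations run from an RR of about 0.87 to about 1.12 at 20% removal. Control dropout alone can carry 1.12 down to 0.95. Those figures rest on assumed values for the share removed for non-use, its quit rate and the actual control dropout. They show that bias in either direction is possible; they do not predict this trial's result.

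**What to change.** In sections 4.3.2 and 6.3.2, drop the principal-strata label. Describe the per-protocol comparison as a descriptive sensitivity analysis and make no causal claim for adherers. This costs a few words and removes the mismatch.

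If an effect in adherers is wanted, add it as a supplementary analysis:
- Define the stratum as compliers: regular ENDS use if allocated to ENDS, none if allocated to control.
- Estimate the complier-average effect in the full analysis set with randomisation as the instrument: the arm difference in quit rate divided by the arm difference in the proportion with regular ENDS use, with a bootstrap confidence interval.
- State monotonicity and the exclusion restriction (allocation acts only through the defined ENDS use).
- Give a rule for missing adherence data, covering missed calls and dropouts.
- Repeat the estimate with exposure defined as any ENDS use. Vaping below 5 days in 7 is still exposure, so the regular-use cut strains the exclusion restriction.

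The costs are a short program, a missing-data rule that the SAP lacks, a wider interval, and assumptions that cannot be fully tested. Disappointment with open-label control allocation also strains the exclusion restriction, so this estimate should remain supplementary. The documents do not support a worked value: the protocol's 30% is ENDS use at 6 months and its 5% is expected purchase, and neither is regular use at a visit.
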